6.5.4 Other Measures

1. Demographics

This assessment will include questions about the participant's ethnicity, age, and sex.

2. CIDI

The Composite International Diagnostic Interview (http://www.hcp.med.harvard.edu/wmhcidi/about.php) (WHO CIDI) will be administered during screening/baseline by a RA who has been trained in the proper administration of this instrument. In addition, each interviewer will undergo a certification check, in which the administration of the instrument is rated by a CIDI trainer. In addition, at least once during the active trial a re-certification check will be completed; interviewers found to be performing below criteria will be provided with additional training as needed.

3. Medical History and Addendum

A medical history will be performed by a MC certified to perform this. In addition, the MC will complete a Medical History Addendum form that includes questions specific to assessing participant eligibility/safety for the present protocol. Any history relevant to cardiac functioning will be provided to the cardiologist responsible for reviewing the participant's ECG.

4. Physical Exam

Performance of a physical exam during screening/baseline will be done at each site by a MC certified to perform physical exams.

5. Smoking History Survey

The Smoking History Survey is a modified version of the Mayo Nicotine Dependence Center Patient Questionnaire (1991) and is administered by the RA. It asks participants how many CPD they smoke, at what age they started smoking, number of years smoking, how many times they have attempted to quit (including methods), when the last quit attempt occurred, their longest period of cigarette abstinence, and if there are other smokers in their household. Information on other non-cigarette tobacco products will also be noted.

6. Fagerström Test for Nicotine Dependence

The Fagerström Test for Nicotine Dependence (FTND) is a brief self-administered assessment of cigarette use patterns (Heatherton et al., 1991). The FTND yields a single overall dependence score and is a standard measure in smoking-cessation trials.

7. Thoughts about Abstinence

Motivation and perceived self-efficacy to change substance use behavior could be impacted by the smoking cessation attempt in the TAU+SCT group. The Thoughts about Abstinence assessment (Hall et al., 1991), which assesses desire to quit, expected success in quitting and estimated difficulty in avoiding relapse, will be completed for alcohol, illicit drugs, and cigarettes, following the schedule outlined in Table 2.

8. Withdrawal Scale for Tobacco (WST)

The WST is a modified version of the Minnesota Withdrawal Scale (Hughes et al, 1991; Hatsukami et al, 1997; Hughes and Hatsukami, 1986). The WST is a self-report questionnaire which asks participants to rate 8 items of withdrawal on a scale from 0=None to 4=Severe. A total score is then computed from the responses to these 8 items. In addition, the 8 items are also examined separately.

9. Medication Compliance

Medication Compliance will be assessed through pill and cartridge counts and self-report according to the schedule provided in Table 2.

10. Smoking Cessation Counseling Compliance

For the TAU+SCT participants, compliance with smoking cessation counseling will be assessed through the number of counseling sessions that the participant attends and completion of homework assignments/session participation.

11. Non-study Smoking Cessation Treatment

For all participants, the use of any non-study smoking cessation treatment, including self-help materials, will be assessed.

12. Study Questionnaire

The Study Questionnaire is a self-report assessment of the relationship between smoking and stimulant use as perceived by the participant. The data from this assessment will be utilized in exploratory analyses.

13. Blood Chemistries

During screening/baseline, blood will be collected in serum separation evacuated venous blood collection tubes. Quantitative analysis will be performed, which will include the following analytes: glucose, creatinine, alanine aminotransferase (ALT/SGPT), aspartate aminotransferase (AST/SGOT), gamma glutamyltranspeptidase (GGT), and blood urea nitrogen (BUN). A prescription topical numbing cream may be offered to all participants prior to the blood draw.

14. Hepatitis Screen

Participants with ALT or AST >2 times normal will be offered the opportunity to have a hepatitis test performed. This test is not requisite for study participation. Blood will be collected in a serum separation evacuated venous blood collection tube (e.g., VacutainerTM) and serum separated according to standard

procedures. Qualitative analysis reporting positive/negative results will be performed for the following analytes: hepatitis B surface antigen, hepatitis B surface antibody, hepatitis B core antibody, and hepatitis C virus antibody.

15. ECG

Twelve-lead electrocardiograms will be performed during screening/baseline according to standard procedures. Ventricular rate (bpm), PR (ms), QRS (ms) and QTc (ms) will be reported on the ECG readouts. The results will be reviewed by a board-certified cardiologist for interpretation and for a clinical judgment about whether the participant is eligible for the study based on the ECG results.

16. Substance Abuse Treatment Status

The Substance Abuse Treatment Status form will be used to assess study candidate's status on study inclusion/exclusion criteria related to substance abuse treatment (e.g., enrolled in outpatient/IOP treatment, etc.). In addition, information regarding pressure to attend treatment, which can be related to substance use outcome, will be assessed.

6.6 Randomization Plan

Eligible participants will be randomized in a 1:1 ratio to the TAU+SCT and TAU arms. The randomization process will be performed by computer at a centralized location. Randomization will be stratified by site and by whether a stimulant-positive UDS result was obtained during baseline/ screening (yes/no). The block size chosen will be adequate to ensure approximate treatment balance. The number in each treatment group will never differ by more than a factor of KB/2 where B is the block size and K is the number of strata.

6.7 Study Treatments

6.7.1 Treatment as Usual + Smoking Cessation Treatment

The four components of the smoking cessation treatment, bupropion XL+ nicotine inhaler, counseling, and contingency management, are described in sections 8.0, 9.0, and 10.0, respectively. Participants randomized to the TAU+ SCT group will be eligible to receive SCT for the full 10 weeks of the SCT intervention irrespective of their concurrent level of participation in drug abuse treatment.

6.7.2 Treatment as Usual

Participants randomized to TAU will participate in substance abuse treatment as typically provided by the CTP. It should be noted that the participants will be recruited from outpatient substance abuse treatment programs that do not provide smoking cessation treatment services on site (see section 6.4.1.1). Participants randomized to TAU in the present trial will, thus, not be deprived of smoking cessation treatment to which they would otherwise have access. Participants in the TAU condition may seek smoking cessation treatment during the course of the trial and any smoking treatment received will be monitored. At the end of the week 28 follow-up visit, the TAU participants will be offered a referral to a specific smoking cessation treatment. An attempt will be made to contact TAU participants who fail to complete the week 28 follow-up visit and a referral to smoking cessation treatment will be offered if the participant is successfully contacted. The specific referral provided will be determined on an individual site basis but will include, at minimum, information about the Smoking Quitline for the state in which the participant resides.

7.0 STUDY PROCEDURES

7.1 Study Overview

Table 2 provides an overview of the participant procedures and assessments.

Assessment/ Procedure	Time Est (Min)	Scrn/ Base		Active Treatment Phase								FU		
			1	2	3	4	5	6	7	8	9	10	16	28
Bupropion XL	5		Х	Х	X	Х	Х	Х	Х	Х	Х	Х		
Smoking Cessat. Counseling	10		Х	Х	Х	Х	Х	Х	Х	Х	Х	Х		
Nicotine Inhaler	5				Х	Х	Х	Х	Х	Х	Х	Х		
Contingency Management	15					2X								
Screening Assessments					ſ		ĺ							
Informed Consent	30	X*												
Demographics	5	X*												
Smoking History Survey	10	X*												
CIDI	90	X*												
Blood chemistry	2	X*												
Birth Control Assessment	2	X*												
ECG	15	X*												
Medical History & Addendum	15	X*												
Substance Abuse Tx Status	5	X*												
Physical Exam	20	X*												
Safety Assessments														
Vital Signs	5	\mathbf{X}^+	Х	Х	Χ	Х	Х	Х	Х	Х	Х	Х		
Weight	1	X*					Х					Х		
Urine Pregnancy Test	2		X*				Χ					Χ		
Adverse Events	5	X*	Χ	Х	Χ	Χ	Χ	Χ	Χ	Χ	Х	Χ		
Prior/Concom Meds	5	X*	Χ	Х	Χ	Χ	Χ	Χ	Χ	Χ	Х	Χ		
HADS	2	X*	Χ	Х	Χ	Χ	Χ	Χ	Χ	Χ	Х	Χ		
Pittsburgh Sleep Quality Index	5	X*					Х					Х		
PRISM -Suicide and Homicide	5	X*					Х					Х		
Efficacy Assessments														
Urine for UDS	2	X^+	2X	2X	2X	2X	2X	2X	2X	2X	2X	2X	Χ	Χ
ASI-Lite	45	X*												
ASI-Lite Follow-up	30											Χ	Χ	Χ
Timeline Follow-Back	10	X*	2X	2X	2X	2X	2X	2X	2X	2X	2X	2X	Х	Χ
Risk Assessment Battery	15	X*										Χ	Х	Χ
BSCS	2	X*	Χ	Х	Χ	Χ	Χ	Χ	Χ	Χ	Χ	Χ	Χ	Χ
CO level	2	X^+	2X	2X	2X	2X	2X	2X	2X	2X	2X	2X	Χ	Χ
Other Assessments														
Fagerström (FTND)	2	X*										Χ	Χ	Χ
Locator Information	5-10	X*										Χ	Χ	
Study Questionnaire	5	X*											7	

Table 2 Overview of Study Assessments and Procedures

CTN-0046 Protocol Version 5.0 – 10-12-11

Assessment/ Procedure	Time Est (Min)	Scrn/ Base		Active Treatment Phase								F	U	
			1	2	3	4	5	6	7	8	9	10	16	28
Thoughts about Abstinence	6	X*										Х		
Withdrawal Scale Tobacco	1	X*				Х	Х	Х	Х	Х	Х	Χ		
Compliance – Medication	5			Х	Х	Х	Х	Х	Х	Х	Х	Х		
Non-study Smoking Tx	1		Х	Х	Х	Х	Х	Х	Х	Х	Х	Х	Х	Х
Assessment Time Est. (min)*		340 [♠]	40	43	43	44	57	44	44	44	44	115	69	64
Administrative Forms														
Study Eligibility	15	X*												
Randomization	5	X*												
Treatment Tracking Form	10		Х	Х	Х	Х	Х	Х	Х	Х	Х	Х		
Compliance – Smk Counseling	2		Х	Х	Х	Х	Х	Х	Х	Х	Х	Х		
CM Tracking Form	5					2X								
End of Treatment Status	5											Χ		

Notes: " X^* " = once during screening/baseline; " X^+ "=at each screening/baseline visit; "X" represents a procedure or assessment performed once per Week; "2X" represents a procedure or assessment performed twice per Week. The estimates provided for the active treatment weeks reflect the total amount of time for the week (i.e., for the two visits combined). Screening/baseline will ideally be completed in three visits, with the average time per visit being approximately 113 minutes.

7.2 Participant Recruitment and Consent

Interested candidates who have been determined by telephone or face-to-face interview to smoke 7 or more CPD, want to quit smoking, are likely to meet the diagnostic criteria for cocaine/METH dependence and other study requirements, and are in (or soon to enroll in) outpatient substance-abuse treatment are invited to receive an explanation of the study purpose and requirements. If still interested after receiving a face-to-face explanation of the study, the candidate is given an opportunity to review, inquire about, and sign the informed consent form.

Any participant who has difficulty understanding the information contained in the consent form is asked to review the misunderstood portion(s) of the consent and discuss them with a research staff member until he or she shows complete understanding of the information and may thus give full consent. Research staff members work closely with the study candidates in an effort to help them understand the requirements of their participation. Persons with literacy problems are assisted to the extent possible. Any participant who is unable to demonstrate understanding of the information contained in the informed consent is excluded from study participation.

7.3 Screening/Baseline

After signing the informed consent form, the study participant proceeds through the screening/baseline phase. Ideally, the screening/baseline procedures will be completed in three visits, but they can be completed in fewer visits or more visits if necessary, with the restriction that randomization can, at the earliest, occur on the seventh day after consent and that at least three screening/baseline UDS results, collected on non-consecutive days, are obtained. Ideally, the screening/baseline procedures will be completed within a two-week time-frame but the allowable time for completion is within 30 days of signing consent. Under certain circumstances a participant will be allowed to re-consent and repeat the screening/baseline procedures if he or she was unable to complete the screening/baseline procedures within the 30-day time-frame. Participants who meet study eligibility and complete screening/baseline as outlined above will be randomly assigned to the TAU+SCT or TAU condition.

7.4 Active Treatment Phase

The active treatment phase is 10 weeks in duration. During this time, participants in both treatment conditions will participate in the substance-abuse treatment typically offered by the CTP. Participants randomized to the TAU+SCT arm will receive individual smoking-cessation counseling consisting of approximately one ten-minute counseling session per week during study weeks 1 through 10. In addition, all TAU+SCT participants will receive bupropion XL (300 mg/day) and, during the post-quit treatment phase, the nicotine inhaler (6-16 cartridges per day ad libitum). Finally, all TAU+SCT participants will receive contingency management in which drawings for prizes are given for smoking abstinence as assessed by carbon monoxide (CO) levels during the post-quit phase of the trial (i.e., weeks 4-10). The TAU+SCT participants will have a target quit smoking day at the end of study week 3. Following the final week 10 visit, TAU+SCT participants will be provided with a 3-day bupropion XL dose taper, in which 150 mg is taken once per day and with a 3 week nicotine inhaler taper. Participants in both conditions will meet with study staff twice weekly to complete study assessments as outlined in Table 2, with the constraint that visits ideally occur on nonconsecutive days.

7.5 Follow-up

The follow-up visits will be conducted at approximately study weeks 16 and 28. The measures to be collected during this visit are delineated in Table 2. There will be a 21-day timeframe in which to complete each follow-up visit.

7.6 Medication and Trial Discontinuation

7.6.1 Medication Discontinuation

An investigator may discontinue a participant's medication if he or she deems it clinically appropriate or, at the discretion of the investigator, for any of the reasons listed below.

- 1. significant side effects that are likely to have been caused by the study medication
- 2. serious or unexpected AEs which would make further study medication dosing not in the participant's best interest
- 3. inability or unwillingness of the participant to comply with the study protocol
- 4. serious intercurrent illness

A participant may discontinue medication anytime s/he wishes. Although the participant may withdraw entirely from the study whenever s/he wishes, s/he will be strongly encouraged to continue attending visits at which safety measures are scheduled to be assessed. TAU+SCT participants who wish to discontinue from study medication early or to withdraw from the study will have their medication discontinued. Any participant who discontinues the study prematurely, regardless of the reason, will be requested to return for a final visit during week 10 to perform the necessary procedures listed in Table-2 and to obtain data for end of study/early termination. Whenever a study participant stops coming to the clinic without notification, staff will make a concerted effort to contact the participant (or the designated contact person if the participant cannot be contacted) to assure that they have had no untoward effects from study participation.

Study participants withdrawn from the protocol secondary to a medical or psychiatric concern will be referred for appropriate treatment. Participants will be asked to sign a general consent for the release of information to the referred health care provider. Study staff may request transportation for emergency treatment of a participant if medically appropriate (e.g., for acutely psychotic or suicidal participants).

7.6.2 Stopping Guidelines

If a participant experiences a seizure while on bupropion XL, he or she will be immediately discontinued from the study medication and will not be eligible to restart on the study medication. Participants who develop elevations of blood pressure >145/95 or heart rate >100 on two consecutive research visits, will be considered as developing clinically significant elevations of blood pressure provided no other contributing causes can be identified other than the study medication. Participants who fail to re-establish normotensive blood pressure readings or normal heart rates, will be evaluated for initiating or readjusting antihypertensive therapy, or have their dose of buproprion XL adjusted downward if necessary to re-establish normotensive blood pressure readings/ normal heart rate, or will be withdrawn from the study medication after a discussion with the study safety officer. Participants with blood pressure $\geq 165/115$ will be seen immediately by qualified medical staff, will have their dose of bupropion XL adjusted downward, or will be withdrawn from the study medication after a discussion with the study safety officer, and will be evaluated for initiating or readjusting antihypertensive therapy. Participants who develop chest pain or shortness of breath on exertion or upon using stimulants during the study will be evaluated by the MC who may order an ECG and follow it up, if necessary, with an exercise test. Any new onset of a clinically significant conduction abnormality or arrhythmia will be discussed with a study cardiologist for a decision on lowering the dose of buproprion XL or withdrawal from the study medication.

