All medications taken by the participant for the 30 days prior to screening/baseline, during screening/baseline, and during the active study will be documented on a Prior/Concomitant Medications assessment (see Table 2). All medications taken by the participant while in the study should ideally be preapproved by the medical clinician whenever possible to avoid interactions with the study drug.

6. Vital Signs and Weight

Vital signs, including blood pressure and heart rate, will be assessed according to the schedule in Table 2. In addition, the participant's weight will be recorded during screening/baseline and at the week-5 and week-10 study visits. Vital signs will be assessed by a trained staff member, either manually or by using a digital blood pressure monitor calibrated within the past twelve months and ideally approved by the Lead Investigator. If the blood pressure is abnormally high or low, it will be repeated one more time approximately 5 minutes later using the same technique. These readings will then be averaged.

7. The Pittsburgh Sleep Quality Index (PSQI)

A potential side-effect of bupropion XL is insomnia (see section 8.7) and smoking cessation can be associated with symptoms of nicotine withdrawal, which includes insomnia. In addition to AE assessments, the potential increase in insomnia will be assessed with the Pittsburgh Sleep Quality Index (PSQI; Buysse et al., 1989). The PSQI is a relatively brief, validated instrument that measures sleep quality. The PSQI will be completed following the schedule outlined in Table 2.

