7.7 Participant Reimbursement

Participants will be reimbursed for their transportation, inconvenience, and time. This reimbursement will be in the form of retail scrip or vouchers. It is recommended that participants receive a total of \$75 for completing screening/baseline. During the active treatment phase, there are two visits per week, one of which is fairly short, comprised of the TLFB, assessing CO level, and collecting urine for the UDS. The other visit during the week will be longer and will include the assessments outlined in Table 2. The recommended reimbursement schedule for these visits is outlined in Table 3. Since the week 10 visit will be substantially longer than all of the other visits, it is recommended that participants be reimbursed a total of \$50 for that visit, as outlined in Table 3. In addition, since the 3- and 6-month follow-up visits are also longer visits, it is recommended that participant be reimbursed a total of \$40 as outlined in Table 3. Using the recommended schedule, a participant could be reimbursed a maximum of \$580. However, participant reimbursement might vary across study sites to take into account local IRB guidelines, as well as special circumstances and geographic differences across sites. The Lead Node should be informed of any changes in level of participant reimbursement.

Table 3. Actinibut schedule for research visits										
Visit	Transportation	Valid urine/CO	Assessment	Total per	Total # of	Grand				
	(\$)	sample (\$)	(\$)	Visit (\$)	Visits	Totals (\$)				
Screening/baseline						75				
Longer visits wks 1-9	10	5	10	25	9	225				
Shorter visits wks 1-10	10	5	0	15	10	150				
Longer visit week 10	10	5	35	50	1	50				
3- and 6-month FU visits	10	5	25	40	2	80				
Total						\$ 580				

Table 3: Reimbursement schedule for research visits

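### The blood-pressure and heart-rate trigger in section 7.6.2 counts research visits, but vital signs are scheduled at only one of the two visits each week

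*Protocol*

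**What the plan says.** Section 7.6.2 (Stopping Guidelines) words the condition as "Participants who develop elevations of blood pressure >145/95 or heart rate >100 on two consecutive research visits". Meeting it, with no other contributing cause identified, marks the elevation as clinically significant. Participants whose readings then do not return to normal are evaluated for antihypertensive therapy, have the bupropion XL dose lowered, or are withdrawn from the medication after discussion with the safety officer. A second tier, at 165/115 or above, has no two-visit condition.

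On visit frequency, section 7.4 states: "Participants in both conditions will meet with study staff twice weekly".

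On measurement, section 6.5.3 states: "Vital signs, including blood pressure and heart rate, will be assessed according to the schedule in Table 2". Table 2 marks vital signs with a single X in each of weeks 1-10, and its notes say that an X "represents a procedure or assessment performed once per Week". Urine drug screen, Timeline Follow-back (TLFB) and CO are marked 2X. At screening, by contrast, vital signs carry the symbol for an assessment made "at each screening/baseline visit".

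On visit content, section 7.7 says of the two weekly visits: "one of which is fairly short, comprised of the TLFB, assessing CO level, and collecting urine for the UDS". It continues: "The other visit during the week will be longer and will include the assessments outlined in Table 2".

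**The concern.** The trigger is counted in one unit, research visits, and the readings that feed it come in another, once-weekly assessments. Table 3, which sets out reimbursement for research visits, lists the shorter visits among them. On the protocol's own usage, a short visit with no scheduled blood pressure or heart rate therefore falls between readings.

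At stake is whether a stated safety rule can be applied as written, and applied alike at about 12 sites. Suppose a participant is above threshold at the longer visits of weeks 5 and 6, with a short visit in between and no extra reading. A site taking the words literally has not seen two consecutive research visits with elevations. A site that counts consecutive vital-sign assessments has. The step after classification, judging whether readings have normalised, depends on the same weekly readings.

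The protocol itself gives reason to care. Section 8.7 lists high blood pressure and rapid heart rate among bupropion side effects, and section 8.9 warns of possible synergistic blood-pressure increases with sympathomimetics. The participants are stimulant-dependent.

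**Working it through.** **Inputs.** Two visits per week for 10 weeks (section 7.4); vital signs once per week (Table 2 and its notes); vital signs not listed at the short visit (section 7.7); item times and weekly totals from Table 2; visit counts from Table 3.

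**Step 1. Is the single X a slip?** Rebuild Table 2's weekly assessment minutes with vital signs counted once (5 min).
- Common items, weeks 1-10: vital signs 5 + adverse events 5 + medications 5 + HADS 2 + urine screen 2×2 + TLFB 10 + craving scale 2 + CO 2×2 + non-study smoking treatment 1 = 38.
- Week 1: 38 + pregnancy test 2 = 40.
- Weeks 2-3: 38 + medication compliance 5 = 43.
- Weeks 4 and 6-9: 43 + withdrawal scale 1 = 44.
- Week 5: 44 + pregnancy test 2 + weight 1 + sleep index 5 + suicide/homicide screen 5 = 57.
- Week 10: 57 + ASI-Lite follow-up 30 + risk battery 15 + FTND 2 + locator 5 + thoughts about abstinence 6 = 115.

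These equal the stated totals (40, 43, 43, 44, 57, 44, 44, 44, 44, 115) in all ten weeks. Counting vital signs twice gives 45, 48, 48, 49, 62, 49, 49, 49, 49, 120, which is 5 minutes too many every week. One caveat: the match takes TLFB's 10 minutes as a weekly total although it is marked 2X. Counting TLFB twice (20 minutes) overshoots by 10 with vital signs once and by 15 with vital signs twice. Of the four combinations, only vital signs once with TLFB at 10 fits.

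**Step 2. Visits.** Table 3 gives 9 longer + 10 shorter + 1 longer in week 10 = 20 visits, hence 20 − 1 = 19 adjacent pairs. Its payments also add up: 75 + 225 + 150 + 50 + 80 = $580.

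**Step 3. Literal reading.** Number the visits so that week w holds visits 2w − 1 and 2w.
- Longer visit always first: readings at visits 1, 3, …, 19. Successive readings are 2 visits apart, so 0 of 19 pairs have both.
- Longer visit always second: readings at visits 2, 4, …, 20. Again 0 of 19.
- Position varies: an adjacent pair arises only when one week's longer visit comes second and the next week's comes first. Each such pair uses up two weeks, so the maximum is 10 / 2 = 5.

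Over all 2^10 = 1,024 placements, only 11 give no adjacent pair. That is not a probability: the placements are not equally likely, and a site may well keep a fixed order.

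**Step 4. Reading as consecutive assessments.** Ten weekly readings give 10 − 1 = 9 pairs, each about 7 days apart.

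**Step 5. What a single reading can trigger in section 7.6.2.** Blood pressure at or above 165/115 does. Blood pressure above 145/95 but below that tier does not, and neither does heart rate above 100.

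**The case against.** A reader might infer that the rule can never fire on the normal schedule. The documents do not support that. It needs both the strictest reading of consecutive and a fixed position for the longer visit, and sections 7.4 and 7.7 fix no order. A missed short visit or an unscheduled reading could also satisfy the rule, and nothing bars an extra reading. There is a sensible working interpretation too: a rule about blood pressure can be taken to mean consecutive visits at which blood pressure is measured.

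Section 7.7 concerns reimbursement, so its account of the short visit need not be exhaustive. Contingency management, which Table 5 places at two visits a week in weeks 4-10, is absent from it. That weakens section 7.7 as evidence, but Table 2's frequency mark and weekly times carry the point without it.

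A reader might also infer that participants are left unprotected, or that two high readings lead straight to a dose cut. Neither follows. The 165/115 tier acts on one reading, there is a separate provision for conduction abnormality or arrhythmia, section 7.6.1 lets the investigator stop medication when clinically appropriate, and adverse events are assessed weekly. Dose reduction is one of several actions, and only after readings fail to normalise. The within-visit repeat in section 6.5.3 confirms a reading but supplies no second visit.

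An elevation first seen at week 10 has no later scheduled vital signs in Table 2. This is minor: section 8.10.1 ends 300 mg dosing at the final week-10 visit, and Appendix A continues adverse-event follow-up for 30 days.

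What stands is that two reasonable readings exist, the text does not choose between them, and one of them is poorly served by the schedule.

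**Conclusion.** The point holds as an internal inconsistency in a safety rule. Section 7.6.2 names two consecutive research visits, while Table 2 supplies blood pressure and heart rate at one visit in two. Usable pairs of scheduled readings over weeks 1-10 number 0 of 19 on the literal reading with a fixed visit order, at most 5 with a varying order, and 9 if consecutive means consecutive vital-sign assessments.

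The fixed order is an assumption, because the protocol does not state one. The counts cover scheduled active-phase readings with every visit attended. That sites could classify the same participant differently follows from the wording; that they will do so is not shown. Nothing in the protocol allows the effect on delivered treatment or on the primary comparison to be quantified, and none is claimed.

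**What to change.** Reconcile section 7.6.2 with Table 2 and section 7.7, so that the visits named in the trigger are visits at which blood pressure and heart rate are scheduled, and so that the text has one meaning at every site. Whether the trigger wording or the schedule changes is for the sponsor's medical staff. No threshold, monitoring rule or dose action is proposed.

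The cost is about one sentence in a protocol amendment, with matching edits where needed. If the sponsor's choice added any readings, Table 2 puts vital signs at 5 minutes each.
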